### **Study Aims**

This randomized controlled trial will test the efficacy of Positive Psychotherapy for Smoking Cessation plus Text Messaging (PPT-S+) compared to a time-matched ST control plus text messaging support for quitting (ST+). We hypothesize that participants in PPT-S+ compared to ST+ will display higher rates of biochemically-confirmed 7-day point-prevalence smoking abstinence across 12 months of follow-up.

#### Method

# Note regarding response to Covid pandemic

The procedures below describe the protocol as implemented prior to March 2020. With social distancing and closure to in-person activities, procedures were modified to accommodate remote enrollment, assessment, and intervention. Those modification are noted as "AFTER MARCH 2020"

# **Study Setting**

All study procedures will take place at the Center for Alcohol and Addiction Studies in the Brown University School of Public Health in Providence, RI or at the Massachusetts General Hospital in Boston, MA. AFTER MARCH 2020: All procedures happened online or by telephone only.

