### **Randomization procedures**

After completing baseline appointment procedures, eligible participants will be randomized to either PPT-S+ or ST+ by the Project Coordinator, who is not involved in conducting assessments or providing treatment. The urn randomization technique[1] will be used to ensure that treatment groups are balanced on gender, PA, and level of cigarette dependence. Research assistants will not be informed of treatment condition assignment. The positive affect subscale of the Center for Epidemiologic Studies – Depression scale (CES-D PA) [9] will be used to measure participants' PA over the past week; this scale has been shown to predict smoking outcome [4] and moderate the effect of PPT-S [19]. Participants' level of cigarette

dependence will be measured via the Fagerström Test for Cigarette Dependence [10, 11]. Condition assignment will be placed in sealed folders, which the counselor will open when participants report to the study center for the initial session of counseling, at which point randomization is considered complete.

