Study Analysis Plan

Positive Psychotherapy for Smoking Cessation Enhanced With Text Messaging: A Randomized

Controlled Trial

NCT02997657

December 22, 2022

[name]., Principal Investigator

Analysis Plan

Initial analyses will use chi-square tests to examine group differences in biochemicallyvalidated, 7-day point prevalence smoking abstinence at each follow-up as well as continuous abstinence across follow-ups. The primary outcome analysis will utilize Generalized Estimating Equations [1, 2] to test the effect of treatment condition on abstinence at 12, 26, and 52 weeks post quit date. GEE is a method of repeated measures analyses for categorical and continuous outcomes that allows for appropriate modeling of covariance structures when observations are correlated across time [3]. The primary, between groups, independent variable in the analysis is treatment group assignment. ST+ will be used as the reference group in this model. The model will contain a linear effect of time as well as the variables included in the urn randomization gender, cigarette dependence, and CES-D PA—following clinical trial analysis recommendations [4]. A second step will test the interaction between treatment condition and time to determine whether relative effects of PPTS+ change over time.

We will also determine if intervention engagement, reduced attraction to smoking, or greater self-efficacy mediates the relationship between PPT-S+ and smoking behavior. A regression analysis will be performed predicting the mediators at session 6 (note that the self-report measures assess strategies used during the quit attempt retrospectively, while attraction and self-efficacy refer to the current moment). Additionally, we will run a second model which adds the mediators to the main effects generalized estimating equations model testing outlined in the previous paragraph. We will use the asymmetric products of coefficients method to calculate the significance of this indirect effect and its 95% confidence interval using the RMediate program [5, 6]. Mediators will be tested sequentially such that strategies will be entered first followed by reduced attraction to smoking and self-efficacy, which serve as more proximal mediators. Follow-up analyses will examine individually each of the four core PPT-S strategies to isolate whether either of these are more important to outcomes.

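### Site and enrolment period (before or after March 2020) are absent from the primary GEE: no bias, but avoidable exposure to chance imbalance and perhaps a little lost power

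*Protocol*

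**What the plan says.** The Protocol's Study Setting names two locations, Providence "or at the Massachusetts General Hospital in Boston, MA", and then records for the later period: "All procedures happened online or by telephone only". Under Randomization procedures, the urn is to keep the arms "balanced on gender, PA, and level of cigarette dependence". It lists nothing else, and the documents do not say whether one urn served both sites.

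The SAP's Analysis Plan states: "The primary outcome analysis will utilize Generalized Estimating Equations [1, 2] to test the effect of treatment condition on abstinence at 12, 26, and 52"; these times are counted in weeks from the quit date. On covariates it says: "The model will contain a linear effect of time as well as the variables included in the urn randomization", meaning gender, cigarette dependence and CES-D PA. A second step tests treatment by time. The SAP mentions neither site nor the March 2020 change.

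Three other parts of the Protocol matter here. Primary outcome measures replaces expired CO plus a saliva cotinine assay with an observed NicAlert test after March 2020. The Timeline reports enrolment restarting from June to September 2020, with follow-up complete by December 2021. Behavioral Treatment Conditions ties follow-up dates to the initially scheduled quit date.

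**The concern.** Enrolment period is fixed before randomisation, as is site for in-person enrollees, and both could plausibly predict abstinence. Catchment differs by city, and delivery, eligibility checks and verification changed in 2020. The SAP already adjusts for the urn variables, citing trial-reporting guidance, and it postdates the planned end of follow-up, so the March 2020 break was known when the model was written.

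Two separate things are at stake:

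- **The primary treatment test.** A chance difference between arms in site or period mix would pass into the estimate unadjusted. If these factors are strongly prognostic, some power is also given up.
- **The time slope.** Later visits fell more often in the remote period, so the linear time term can mix relapse with a change in how abstinence was verified.

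**Working it through.** **1. The plan's own power figures.** Two-sided 5%, 80% power and 1:1 allocation are assumed where not stated.

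- Continuous abstinence, 20% v 8%, continuity-corrected: 147 per arm, 294 in total, against the stated 298.
- The GEE figure of 272 depends on a covariance matrix that is not given. An asymptotic calculation (logit link, treatment plus linear time, sandwich variance, rates 45/30/25% v 30/17.5/12.5%) returns 272 at an exchangeable correlation of about 0.62. The range is 184 to 298 for correlations of 0.3 to 0.7. So 272 is plausible but cannot be checked exactly.
- Evaluable sample: 340 × 0.9 = 306. Scaling the stated power gives 2.80 × √(306/272) − 1.96 = 1.01, or about 84%.

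**2. Chance imbalance.** Simple 1:1 allocation with no balancing on the factor; the 95% limit is 1.96 × √(4p(1−p)/N).

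- Site, p = 0.5 (assumed): N = 340 gives 1.96 × √(1/340) = 10.6 points; N = 306 gives 11.2 points.
- Late enrolment: about 37.5 months to mid-March 2020 plus 4 months gives 4/41.5, roughly 10% if accrual was even. N = 306 gives 1.96 × √(0.36/306) = 6.7 points.
- Approximate shift in the treatment log odds ratio (imbalance × log covariate odds ratio), at these N = 306 limits:
  - Odds ratio 2: site 0.112 × 0.693 = 0.078 (a factor of 1.08, about 35% of the standard error of 0.226); period 0.047 (about 21%).
  - Odds ratio 3: site 0.123 (a factor of 1.13); period 0.074 (1.08).

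**3. Power without and with adjustment.** Simulated GEE, N = 306, 4,000 runs per case, planned marginal rates held fixed, within-person correlation about 0.61, site and period as two binary covariates sharing one odds ratio. The urn covariates are left out of both models, so read only the differences.

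| Covariate OR | Site 50/50, 10% late | Site 30/70, 30% late |
|---|---|---|
| 1.0 | 85.0% → 85.2% | not run |
| 1.5 | 85.6% → 85.9% | 85.3% → 86.5% |
| 2 | 85.4% → 87.3% | 85.7% → 87.5% |
| 3 | 84.4% → 88.7% | 85.3% → 90.4% |

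Monte Carlo error is √(0.85 × 0.15/4000), about 0.6 points per entry. A separate 1,500-run simulation with site alone gave gains of 0.6, 0.7 and 1.9 points at odds ratios 1.5, 2 and 3. Its starting power of 90% to 93% is above the 84% in step 1, so it reflects a weaker correlation than 272 implies. Taken together, the gains are about 0 to 1.5, 1 to 2 and 1.5 to 5 points.

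**4. Where the gain comes from.** At odds ratio 2 (50/50, 10% late) the log odds ratio moves from 0.674 to 0.706 and its standard error from 0.226 to 0.230. The ratio rises from 2.98 to 3.07 although the standard error grows.

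**5. Type I error.** Under the null, rejection is 4.5% to 5.4% without the covariates and 4.4% to 5.6% with them.

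**6. Visits in the remote period.** Assume even accrual and a quit date about 3 weeks after baseline (counselling within a week, session 3 two weeks later). Visits then fall 15, 29 and 55 weeks after baseline, or 3.45, 6.67 and 12.66 months.

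- 12 weeks: (3.45 + 4)/41.5 = 18%
- 26 weeks: (6.67 + 4)/41.5 = 26%
- 52 weeks: (12.66 + 4)/41.5 = 40%

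**The case against.** The strongest reply is that nothing is broken. Randomisation protects the test, the SAP follows a stated principle of adjusting for the balancing variables, and no document shows that site or period predicts abstinence. With post-restart enrolment at roughly 10%, any benefit is small. Choosing new primary covariates after data collection also invites a charge of data-driven selection. All of this stands. It limits the point to an optional improvement and makes the timing of the change matter.

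A reader might infer several stronger things that the documents do not support:

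- **That the unadjusted effect is biased toward zero.** The smaller log odds ratio reflects non-collapsibility. The planned model targets an effect averaged over site and period, and adjustment changes that estimand.
- **That precision is being thrown away.** The standard error does not fall with adjustment.
- **That the urn was wrong to omit period.** Randomisation began in 2017, before the change could be known.
- **That site is known for everyone.** Late enrollees were wholly remote, and no rule assigns them to a city.
- **That the verification change undermines the treatment contrast.** In the primary model time is a nuisance term, and calendar date is independent of arm in expectation. The treatment-by-time step would be distorted chiefly if the method change acted differently by arm, and a main-effect indicator would not repair that.

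**Conclusion.** The omission is real and minor. The primary test remains valid. What is lost is protection against a chance imbalance that, at its 95% limit for site and a covariate odds ratio of 2, would move the treatment estimate by about a third of its standard error, together with 0 to 5 points of power depending on a prognostic strength that the documents do not give. If the factors do not predict abstinence, adjustment costs essentially no power. These sizes rest on the assumed odds ratios, site share, accrual pattern and correlation, and on the urn not having been run separately by site.

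The time slope is a separate matter of interpretation: the remote share of visits more than doubles between 12 and 52 weeks, so the slope should not be read as relapse alone.

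**What to change.** - **Primary GEE (SAP, Analysis Plan).** Add one baseline factor with levels Providence, Boston and remote (enrolled after March 2020). This resolves the missing site rule. Keep treatment as the single tested effect and state that the odds ratio is conditional on this factor too. The simulation used two binary covariates; this factor also takes two degrees of freedom, but its gain was not simulated separately.
- **Timing.** If outcomes by arm were already seen when the change is made, keep the planned model as primary and report the adjusted one beside it as a sensitivity analysis.
- **Time slope.** When interpreting it, add a visit-level indicator for whether the scheduled follow-up date, counted from the initially scheduled quit date, fell after March 2020. Define it for every participant at every visit. Never code it from whether or how verification was done: confirmation applies only to self-reported abstainers, so such coding would condition on the outcome.
- **Treatment-by-time step.** Check a treatment-by-period interaction as a sensitivity analysis.

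The cost is SAP wording, two or three degrees of freedom and a slightly more conditional odds ratio. It uses enrolment site and dates, with no new data collection.

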# **Participants**

A total of 340 participants will be enrolled in the study over an approximately 3-year period, which started in February 2017. Participants must meet the following criteria: 1) be at least 18 years of age; 2) smoke at least 5 cigarettes per day for longer than one year; 3) be willing to use the nicotine patch; 4) rate the importance of quitting smoking a 5 on a 0 to 10 scale (where  $10 = extremely\ important$ ); 5) have an active, text-capable cell phone and be willing to send and receive text messages for the duration of the intervention. Participants who do not have unlimited texting will be compensated an additional \$20 to offset any additional costs on their cell phone bill. Participants will be excluded from the study, if they meet any of the following criteria: (1) are currently experiencing psychotic symptoms, affective disorder, or substance use disorder other than nicotine dependence; (2) are concomitantly using other pharmacotherapies for smoking cessation; (3) are pregnant or nursing, or (4) have any contraindications to the use of transdermal nicotine patch.

AFTER MARCH 2020: To confirm smoking status at baseline, participants were sent a NicAlert test strip for saliva testing of cotinine and completed the test while being observed during a Zoom call with a research assistant. A test positive for cotinine was required for enrollment. The limit of detection for the NicAlert strip is 30 ng/mL

### **Outcome Variables**

### **Primary outcome measures**

The primary outcome for testing intervention efficacy is biochemically verified 7-day point-prevalence abstinence at 12-, 26-, and 52-week follow-ups. We will also use the Timeline Followback [3, 4] to assess time to first lapse and relapse and continuous abstinence from smoking. Participants will provide breath samples for expired carbon monoxide (CO) analysis at baseline, each treatment session, and each follow-up interview. At 12-, 26-, and 52-week follow ups self-reported smoking abstinence with no other use of nicotine-containing products—including nicotine replacement therapy and electronic cigarettes—will be verified by both CO (cutoff value of  $\leq$ 4ppm) [5] and saliva cotinine radioimmune assay analysis (cutoff value of  $\leq$  15 ng/ml) [6]. For those reporting smoking abstinence, but with past 7-day use of other nicotine containing products, abstinence will be verified only by CO. Continuous smoking abstinence will be defined as self-reporting no cigarettes smoked since quit date with abstinence biochemically confirmed at each follow-up or confirmed by collateral reports from significant others.

AFTER MARCH 2020: Self-reported abstinence was biochemically confirmed with a NicAlert test which was sent to the participants how and self-administered while being observed by the research assistant on Zoom.

# Secondary outcome measures and assessment points

The secondary outcome of this study is to determine if the effect of PPT-S+ on smoking outcome is mediated by greater use of PPT-consistent strategies, reduced attraction to smoking, or greater smoking cessation self-efficacy. Participants will complete a Treatment Strategies Questionnaire at sessions 4-6 to assess frequency of general smoking cessation strategies usage, including planning for high-risk situations, and PPT-consistent strategies. PPT-consistent strategies are worded in a general way so that participants in each condition can rate how often they have done that activity; PPT-S consistent strategies include intentionally focusing on mental health benefits of quitting, using signature strengths, savoring positive experiences, and engaging in positive social interactions [2]. For those in PPT-S+, we also will have a record of how many PPT-S+ interactive texts were responded to, which will be coded according to whether the exercise was completed. In both conditions, we will calculate a variable reflecting the percent of responses to interactive messages. Smoking cessation self-efficacy will be measured at each counseling session using a well-validated 9-item scale [7]. Residual attraction to smoking (e.g., "Does smoking have any attraction for you now?") will be assessed at the end of the treatment (i.e. 4 weeks after quite date) with a validated 3-item scale [8].

#### **Recruitment Procedures**

Participants will be recruited through advertisements localized to the greater Providence, RI and Boston, MA region on public transportation, newspaper, radio, and local television. The advertisements give potential participants the information to call or text the study phone number or visit the study website for more information. Additionally, a social media campaign will be used including an interactive study website. Participants will have the opportunity to complete an online screener to determine eligibility.

#### **Procedure Overview**

Prospective participants will be screened either by telephone or by an online web portal system according to the inclusion criteria. Participants meeting inclusion criteria will be invited to the study sites to complete a baseline interview to confirm eligibility. Eligible participants will be randomized and start counseling within a week of the baseline interview. Quit date will be scheduled for all participants to coincide with their third session of counseling. Participants will be assessed on a variety of interview, self-report, and biochemical measures at baseline and each treatment session, and at 12, 26, and 52 weeks after quit date. Interviewers conducting follow-ups will not be aware of participants' assigned treatment condition.

AFTER MARCH 2020: All assessments and counseling occurred by telephone or Zoom videoconferencing.

#### Assessments

### **Baseline Assessment**

At baseline, participants will complete written informed consent. They will then complete written questionnaires and interviews to determine eligibility for the study, including a medical history screen. A blood pressure reading will be taken to exclude participants who have elevated blood pressure that would require medical treatment. Because nicotine patch is contraindicated for nursing and pregnant women, all women of childbearing age will be administered a pregnancy test to ensure non-pregnant status. If pregnant, they will be referred to other treatment. Participants will be paid \$20 for completing the baseline assessment.

AFTER MARCH 2020: No blood pressure readings or pregnancy tests were done.

### **Follow-up Interviews**

Participants will return to the study sites to complete in-person follow-ups at 12, 26, and 52 weeks after their scheduled quit date. To increase retention, participants will be paid up to \$120 for completing assessments according to the following schedule: \$35 for 12-week follow-up (plus \$20 for those without unlimited texting), \$35 for the 26-week follow-up, and \$50 for the 52-week follow-up. These payments are not contingent upon smoking status. When necessary, relatives or friends listed by participants as potential locators will provide information about participants' whereabouts.

### **Randomization procedures**

After completing baseline appointment procedures, eligible participants will be randomized to either PPT-S+ or ST+ by the Project Coordinator, who is not involved in conducting assessments or providing treatment. The urn randomization technique[1] will be used to ensure that treatment groups are balanced on gender, PA, and level of cigarette dependence. Research assistants will not be informed of treatment condition assignment. The positive affect subscale of the Center for Epidemiologic Studies – Depression scale (CES-D PA) [9] will be used to measure participants' PA over the past week; this scale has been shown to predict smoking outcome [4] and moderate the effect of PPT-S [19]. Participants' level of cigarette

dependence will be measured via the Fagerström Test for Cigarette Dependence [10, 11]. Condition assignment will be placed in sealed folders, which the counselor will open when participants report to the study center for the initial session of counseling, at which point randomization is considered complete.

#### Details of the intervention and control

# **Nicotine Replacement Therapy**

All participants will be provided an eight week supply of transdermal nicotine patch with initial patch dosage (7mg, 14mg, or 21mg) based on their smoking rate at baseline following the product recommendations.

#### **Behavioral Treatment Conditions**

All participants will receive a common core of behavioral smoking cessation counseling which includes instructions for using the nicotine patch, a text messaging support program, and 6 weekly sessions of counseling. The first session of counseling lasts about 50 minutes with the remaining sessions lasting about 35 minutes. All participants have a target quit date set for session 3 (2 weeks post initial counseling session). Participants who relapse to smoking after session 3 may set a new quit date, but the initially scheduled quit date remains as the date on which other study procedures (e.g., follow-up visits) are based.

### **Counselor Qualifications, Training, and Supervision**

Qualifications for study counselors are a master's degree or above with experience in behavioral health counseling. All counselors will conduct both PPT-S+ and ST+ sessions. Counselors will participate in approximately 20 hours of training prior to delivering interventions. Training will include an overview of PPT-S+ and ST+ protocols, review of manuals and handouts, and practice role-play exercises along with selected readings on treatment of tobacco use and positive psychology. Additionally, counselors will be asked to listen to several of the audiotape samples from the randomized controlled pilot study and will conduct mock sessions with one another.

Counselors will participate in weekly supervision sessions. All sessions will be audiotaped, and a session from every fifth case will be rated for adherence and competence. Counselors will be provided feedback on adherence to manual components, level of skill delivering components, use of appropriate structure and focus, empathy and facilitation of the therapeutic alliance. Counselors who deviate from the protocol will be monitored closely and may be asked to role-play protocols until their performance meets acceptable standards.

Treatment integrity for PPT-S+ and ST+ as described in the treatment protocols will be assessed with adherence checklists. Ratings of treatment adherence will be conducted by a research assistant unaffiliated with treatment delivery using checklists containing each of the critical topics of the treatment session outlines in each condition. Checklists will be summed to indicate the proportion of intended topics that were covered in a treatment session. Session tapes will be rated only after participants' follow-ups are completed. A second research assistant will rate one-fifth of sessions as a reliability check.

